4.3 Patient course

Patients identified by the attending surgeon as eligible for inclusion (see in- and exclusion criteria previously mentioned) are invited to participate. Patients who express an interest in participating will be given written and oral information on the purpose, nature and implications of study-participation. Information and inclusion of participants will be conducted in accordance with the guidelines of The Health Research Ethics Committee System in Denmark, from which approval will be sought.

Prior to surgery at the Center for Spine Surgery and Research, Middelfart, study subjects will undergo assessment and quantification of pain sensitivity using a standardized QST battery and pain drawing (figure 1). Patients will also be asked to fill-out multiple questionnaires (basic personal information, EQ-5D, OSWESTRY, SF-36, VAS-leg/-back, etc.) as stated in section 5.1 Data collection.

The standardized QST battery consist of 3 different modalities, covering different measurements of pain perception and multiple types of pain stimulus. Initially patients will undergo a simple Pressure Pain Test (PPT) using an electronic/analog pressure pain algometer at the thenar eminence of the hand and the most painful site of the lumbar area, as previously described (25, 32). Patients are instructed to indicate when pain is felt, Pressure Pain Detection Threshold (PPDT). Pain intensity at 140% of PPDT, the Pain Response (PR) is subsequently rated on a VAS. Immediately following both the thenar and lumbar test, a temporal summation test will also be performed. Using a 51,2g PinPrick stimulator, initially a single stimulus will be given, and the patient asked to rate the pain. Thereafter 10 repetitive stimuli will be given and the patient asked to rate the pain of the last stimulus. Temporal summation can then be calculated as the difference in pain following a single stimulus vs the last in a series of 10.

To test for deep mechanic pain sensitivity, a pneumatic double-chamber cuff will be placed around: (i) the arm and (ii) the leg. Cuff inflation rate will be constant and the pain intensity registered continuously on a visual analogue scale (VAS); thresholds of detection and tolerance will be recorded.

Furthermore, patients will undergo a Cold-Pressor Test (CPT) using a water-tub containing refrigerated water at 0-2°C in which they are to submerge their non-dominant hand to the wrist for 3 minutes. During the CPT, pain response will be monitored using a continuous VAS, controlled by the patient. For individuals who fail to tolerate the entire 3 minutes, time of withdrawal will be recorded. Immediately following the CPT, patients will, once again, be tested using the PPT described above. This is performed to analyze Conditioned Pain Modulation

(CPM) in the central nervous system. Following a short break (approx. 3-5 min.), patients will receive an injection of sterile hypertonic saline at the infraspinatus muscle of the scapula. Once again pain response will be measured using a continuous VAS.

	Pain Detection Threshold	Pain Tolerance Threshold	Pain Response	Continuous Pain Response	Complex Pain Modulation
Mechanical	PPT		PPT		PPT
Thermic		СРТ		CPT	СРТ
Chemical			NaCl	NaCl	

All patients participating in the study will undergo standard operative treatment, either open or microscopically, at Center for Spine Surgery and Research, Middelfart, and scheduled for an outpatient clinical control with a physiotherapist 4-6 weeks post-operative. The examination, assessment and treatment offered are not affected by study participation.

4.4 Facilities

The staff at Center for Spine Surgery and Research, Middelfart will perform initial consultation, assessment, surgery and post-operative treatment.

The Ph.D.-student will perform the initial recruitment and the standardized QST.

5 Data & Statistics

Clinical Tools	At inclusion and pre- operative	6-weeks ambulatory control	6-month ambulatory control	12-month ambulatory control
EQ-5D	х	Х		Х
Oswestry Disability Index (ODI)	х			Х
SF-36	Х			Х
Standardized QST	Х	Х	Х	
VAS-leg and VAS-back	х	Х	Х	X
Pain drawing	х	Х	Х	X
DaneSpine questionnaire		Х		Х

5.1 Data collection

5.2 Data handling

Collected data will be processed and stored by the research secretariat at Center for Spine Surgery and Research, Middelfart, using EPI-data and in agreement with the requirements of the Danish Data Protection Agency.

5.3 Statistics

Data will be analyzed according to their type using STATA, i.e.; categorical data will be presented by means of frequencies and related percentages; continuous data will be displayed by means of descriptive statistics (mean, standard deviation, number of observations, minimum, median, maximum).

5.3.1 Sample size rationale

Based on the data gathered during the initial pilot-study, reverse power-calculations have been performed on variables showing tendency towards significance in Spearman's Rank Correlation and Pearson's Correlations. Based on these calculations an estimated study group of 70-100 patients is needed to secure substantial data for statistical significance.

6 Quality control and quality assurance

The study will be registered at the Ethical Committee of Southern Denmark and the Danish Data Protection Agency.

All patient data, including information on private matters or other confidential information, will be strictly confidential and stored according to the Danish Open Administration Act, the Danish Act on Processing of Personal Data and the Health Act.

The study will be performed in accordance with the guidelines recommended by STROBE (STrenghtening the Reporting of OBservational studies in Epidemiology).

7 Ethics

This study will be a clinical trial conducted according to Danish ethical principles as well as the Declaration of Helsinki.

We take the patients' rights into account, as participation in the study is completely voluntary and can only take place after receiving both oral and written information about the study. Furthermore, all participants must sign a consent form. At any time during the study, the participants can withdraw their consent orally, in writing or by any other clear notification. If the participant chooses to withdraw the consent it will not affect the right to any current or future treatment.

The participants are entitled to bring a member of the family or friend to the informative interview and will be given 24 hours to consider participation before signing the consent form. The Informed Consent form will be signed by all participating patients and stored at the Center for Spine Surgery and Research, Middelfart.

According to the Danish Open Administration Act the participants are entitled to access the research protocols and documents concerning the patient's own participation in the study. This opportunity is available for two years after completion of the study.

The patients have the right to complain and apply for compensation according to the Act on the Right to Complain and Receive Compensation within the Health Service.

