- Can QST be used to identify patients with a change in pain perception and potential abnormal response to painful stimuli?
- Can QST be used to reflect patients pain perception using self-reported questionnaires on pain?
- Is there a correlation between quantitative sensory testing of experimental pain responses and clinical outcome of surgery in LDH patients assess using standardized questionnaires?

4 Methods

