4.1 Design

The experimental study design will be a prospective cohort study in accordance with the STROBE guidelines (31). A pilot-study including 15 male and 15 female participants have been conducted in order to assess the setup of QST and to evaluate if PET/CT were a viable way of identifying pain perception and potentially quantifying it. In accordance with previous protocol, data have now been reviewed and evaluated, leading to a modified setup with QST and a dismissal of PET/CT.

Based on the results gained from the pilot-study, it has been found reasonable to continue with further study participants in the QST-part of the study. Therefore, a continuance of QST measurements will be performed on further 70 patients as stated in detail below.

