4.2.3 Subject withdrawal

- The patient has some other clinically significant medical condition that in the opinion of the investigators could impact the patient's ability to successfully complete the trial or otherwise interfere with outcomes
- The patient has, during the follow-up period, received medication or invasive intervention that in the opinion of the investigators could impact the patient's ability to successfully complete the trial or otherwise interfere with outcomes

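### The 70-100 sample size comes from pilot correlations selected for near-significance in 30 participants, so it does not support the claim that the number secures statistical significance

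*Combined protocol and SAP*

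**What the plan says.** The whole sample size argument is in section 5.3.1. It starts from the pilot ("Based on the data gathered during the initial pilot-study"), reports that "reverse power-calculations have been performed on variables showing tendency towards significance" in Spearman and Pearson correlations, and concludes that "an estimated study group of 70-100 patients is needed to secure substantial data for statistical significance".

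Section 4.1 gives the pilot size ("A pilot-study including 15 male and 15 female participants have been conducted") and the recruitment still to come ("a continuance of QST measurements will be performed on further 70 patients"). It does not say whether the 30 pilot participants count towards the 70-100.

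Section 3 asks, among other questions: "Is there a correlation between quantitative sensory testing of experimental pain responses and clinical outcome of surgery". Neither 5.3 nor 5.3.1 names a QST variable, an outcome, a target correlation, alpha, power, the p-value that counted as near-significant, or the number of pilot participants with paired data.

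**The concern.** For a fixed number of pairs, the p-value of a correlation and its absolute size carry the same information. If pilot correlations are kept because their p-value was small or nearly small, their size is already largely decided by the pilot n and the cut-off. A sample size computed from them inherits that. Pilot variables that showed no such tendency gave no input.

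Where the true correlation is modest, only the pilots that overestimate it pass the filter. The resulting n then looks sufficient when the real power is below nominal. What is at stake is how a null result is read: if the plan says that the number secures significance, a non-significant correlation may be taken to show that QST does not predict surgical outcome, when the study may simply have been too imprecise to tell.

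**Working it through.** **Inputs from the plan.** Pilot n = 30 (4.1); selection by near-significance (5.3.1); stated n = 70-100 (5.3.1); 70 new patients (4.1).

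**Assumptions, because the plan is silent.** Two-sided alpha 5%, 80% power (90% as a variant), 30 complete pairs, pilot p between 0.05 and 0.15 (or any p < 0.15), and the observed pilot correlation entered directly into the calculation.

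**1. The plan's figure.** It cannot be reproduced, because r, alpha and power are not given. It can only be worked backwards, with r = tanh((1.960 + 0.842)/√(n − 3)):

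- n = 70: tanh(2.802/√67) = 0.330. In 30 pairs t = r√(28/(1 − r²)) = 1.85, p = 0.075; pilot 95% CI −0.03 to 0.62.
- n = 100: tanh(2.802/√97) = 0.277. In 30 pairs t = 1.53, p = 0.138; pilot 95% CI −0.09 to 0.58.
- At 90% power the implied values are r = 0.377 (p = 0.040) and r = 0.318 (p = 0.087).

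**2. From pilot p-value to n.** With 28 degrees of freedom, r = t/√(28 + t²), then n = (2.802/atanh r)² + 3, rounded up:

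| Pilot p | t | r | atanh r | n, 80% power | n, 90% power |
|---|---|---|---|---|---|
| 0.05 | 2.048 | 0.361 | 0.378 | 58 | 77 |
| 0.10 | 1.701 | 0.306 | 0.316 | 82 | 109 |
| 0.15 | 1.480 | 0.269 | 0.276 | 106 | 141 |

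The true correlation does not enter. Variants of 58-106 for the same p-values: 62-113 with a Spearman variance factor of 1.06, 47-85 one-sided, 48-87 if only 25 pairs were complete.

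**3. What selection does to real power.** Pilots of 30 bivariate normal pairs were simulated for several true r. Those passing the filter were kept, n was computed from the observed |r|, and the power of the true r at that n was averaged.

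| True r | Median n, p 0.05-0.15 | Real power | Median n, p < 0.15 | Real power |
|---|---|---|---|---|
| 0 | about 81 | – | 70 | – |
| 0.1 | about 80 | 14% | about 65 | 13% |
| 0.2 | about 78 | 43% | about 57 | 33% |
| 0.3 | about 77 | 76% | about 47 | 55% |

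Nominal power was 80% throughout. At true r = 0.3 the mean |r| among picked pilots is 0.315 in the closed window and 0.411 with p < 0.15. Over six assumed filters (0.05 to 0.10, 0.15 or 0.20; below 0.10, 0.15 or 0.20), real power at r = 0.2 is 28-47%.

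**4. Power at the stated numbers, however they were obtained.** Power = Φ(atanh(r)·√(n − 3) − 1.960):

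- r = 0.20: n = 70 gives Φ(1.659 − 1.960) = 38%; n = 100 gives Φ(1.997 − 1.960) = 51%.
- r = 0.25: 55% and 71%.
- r = 0.30: n = 70 gives Φ(2.534 − 1.960) = 72%; n = 100 gives Φ(3.048 − 1.960) = 86%.

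**5. Precision at the stated numbers.** 95% CI = tanh(atanh(0.30) ± 1.960/√(n − 3)), with atanh(0.30) = 0.3095:

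- n = 70: tanh(0.3095 ± 0.2395) = 0.07 to 0.50.
- n = 100: tanh(0.3095 ± 0.1990) = 0.11 to 0.47.

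**The case against.** The strongest reply is that the plan gives no cut-off and does not say that clearly significant pilot variables were left out. The result that n is the same at any true correlation follows by construction from closing the p-window at both ends. With p < 0.15 it fails: the median n falls from 70 to about 47 as true r goes from 0 to 0.3. This stands, so the invariance is claimed only for the closed window. The bias remains under every filter tried, and the open one gives lower real power.

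Second, any n can be worked back to some r and some pilot p. A deliberate target of about 0.28-0.33 would also give 70-100, and at 90% power the implied pilot p of 0.040 lies below 0.05. This stands too: the back-calculation shows consistency, not origin.

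Third, 30 participants need not mean 30 pairs, and 5.3.1 does not say which correlations were used. They may relate QST to self-reported pain, the second question in section 3, and not to surgical outcome. Both are unknown and change the figures, not the selection problem.

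Fourth, a reader might infer that the study is underpowered and must recruit more. The documents do not support that. They state no true or clinically relevant correlation, power at r = 0.30 is 72-86%, and if the pilot counts, 30 + 70 = 100 exceeds the 85 needed for 80% power at r = 0.30 before any loss.

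**Conclusion.** The point holds in limited form. Section 5.3.1 describes a sizing rule that selects its own effect size by significance in a small pilot. That rule cannot support the statement that 70-100 patients will deliver significance. If true correlations are near 0.2, a number obtained this way has real power of about 43% (closed window) or 33% (p < 0.15) against a nominal 80%. Near 0.3 the figures are 76% and 55%. They rest on two-sided 5%, 30 complete pairs and the assumed cut-offs.

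Three stronger readings go too far: that the calculation returns the same n for any correlation under any cut-off; that 70-100 is known to be an artefact of the pilot; and that 70-100 is too few. What the plan lacks is a basis for its assurance, and a statement of what 70 or 100 patients can and cannot show.

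**What to change.** In 5.3.1, remove the statement that the number secures statistical significance, describe 70 new patients as a number set by feasibility, and give its precision. Suggested text:

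> With 70 (100) patients with outcome data, the 95% CI around a correlation of 0.30 is 0.07-0.50 (0.11-0.47). A non-significant correlation is not evidence of no association.

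In 4.1 and 5.3.1, state whether the 30 pilot participants count towards the 70-100. If they do, either test variables picked from the pilot in the 70 new patients only, so that the same data do not both choose and test them, or report all QST variables in the pooled 100 with multiplicity acknowledged.

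The cost is a paragraph and the loss of the claim of assured significance. No new patients are needed.
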